1. INTRODUCTION

An association has been observed between pneumonia and currently marketed ICScontaining medications relative to non-steroid containing medications among patients with COPD [Ernst, 2007, Crim, 2009; Drummond, 2008; Spencer, 2011; Singh, 2010]. The risk factors for development of pneumonia, including serious pneumonia requiring hospitalization, have been well-characterized in clinical and observational studies and include older age, current smoking, low BMI, certain chronic co morbid conditions (e.g. dementia), higher levels of dyspnoea, and markers of COPD disease severity [Calverley, 2011; Crim, 2009; Mannino, 2009; Müllerova, 2012].

In clinical trials, serious pneumonia was defined as any pneumonia that resulted in death, immediate risk of death (investigator judgment), or hospitalization or prolonged existing hospitalization. In the fluticasone furoate (FF)/vilanterol (VI), an increased incidence of pneumonia, including serious pneumonia was observed with the use of FF/VI compared with VI monotherapy in two one-year-long exacerbation studies (study HZC102970 and study HZC102871). In addition, there were reports of fatal pneumonia in the FF/VI 200/25 treatment group.

In previous studies within the same class of medicines, there was approximately a 1.5 to 2-fold increase in the risk of serious pneumonia, the ICS-containing medication as compared to long-acting beta-agonist (LABA) monotherapy (30 vs. 55 pneumonia episodes per 1,000 person years for 500/50 fluticasone propionate / salmeterol combination [SFC] and 50 salmeterol, respectively [Crim, 2009]. There was no increase in the risk of pneumonia fatality, and results suggested a reduction in mortality in patients taking FSC relative to placebo, but did not achieve statistical significance [Calverley, 2007]. A similar two-fold increase was seen in the two, one-year long studies of FSC vs. SAL studies (data not shown).

In the FF/VI development program, the risk of serious pneumonia was almost three-fold greater for the FF/VI relative to the VI treatment groups (34.9, 37.0, and 33.6 per 1,000 person years for 50/250, 100/25, and 200/25 FF/VI versus 12.1 per 1,000 person years in 25 VI). In addition, inconsistencies in incidence of fatal pneumonia events between the two FF/VI exacerbation studies were noted; however, the low absolute number of fatal events precludes an accurate assessment of the risk or an evaluation of a dose response relationship due to low precision.

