5.2.1. New User Study Population

Based on the treatment guidelines, we expect the potential for differences in COPD severity between treatment groups that require adjustment in the analysis. For the treatment of COPD, there is a consensus document on the treatment paradigm for patients with COPD [GOLD, 2009]. A LABD is recommended as an initial maintenance treatment in patients with COPD, including long-acting antimuscarinics (LAMA) or long-acting beta-agonists (LABA). If the disease severity warrants, adding additional therapy (a second bronchodilator or ICS) is recommended. However, an internal unpublished analysis estimated that ~10% of patients at COPD diagnosis are prescribed triple therapy (LABA, LAMA, ICS) during the period 2008 -2009.

CPRD-GOLD data are available through December 22, 2011 with the 1Q2011 data load. HES data are available through August 2011 with the latest data load. Therefore, patients are examined to identify new users between January 2002 and December 31, 2010 to allow for time in the cohort after being identified as a new user and prior to censoring of available data. If the data availability changes, the study period will adjust accordingly in the analysis plan.

The **Baseline Period** is the one-year period prior to Cohort Entry Period to confirm new user status and evaluate patient characteristics of interest.

Identifying New Users

For the purposes of this study, a new user will be defined as someone who has not used medications of interest (ICS-containing or LABD containing medications) in the year prior to a new prescription of a medication of interest (ICS-containing of LABD). The one-year period of no use is referred to a washout period rather than requiring no use of these medications ever in the patient's history. New users of ICS-containing medications and new users of LABD would be identified separately, and are described in Figure 2.

The following patients would not be considered new users:

- New users of triple therapy (LABA/LAMA/ICS) in three single inhalers or ICS/LABA inhaler plus LAMA
- Patients who step up from LABD to ICS/LABA combination therapy in a single device (based on definition of a new user, they have LABD in the history)

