ICS New Users. Patients will have at least one prescription for ICS-containing medications from January 2002 (the earliest use) until December, 2010 preceded by a year of no use of ICS-containing medications (ICS monotherapy or ICS/LABA fixed dose combination or ICS/SABA) or LABA or LAMA prior to the new user prescription. At Cohort Entry, Patients who are new users of ICS monotherapy or ICS+LABA or ICS+LAMA in separate inhalers could be included as new users. However, patients prescribed new use of triple therapy (ICS, LAMA, LABA) would be excluded from this analysis.

LABD New Users. Patients will have at least one prescription for LABA or LAMA (but not both) from January 2002 (the earliest use) until December, 2010 preceded by a year of no use of ICS-containing medications (ICS monotherapy or ICS/LABA fixed dose combination or ICS/SABA) or LABA or LAMA prior to the new user prescription.

By definition, patients prescribed new use of triple therapy (ICS, LAMA, LABA) would be excluded from this analysis.

Algorithm to Identify New Users. To identify new users, the following algorithm would be employed. First, patients will be evaluated to see if identify their first prescription of LABD in the analysis period (2002 through 2010). Next patients would be evaluated to see if they are new users of ICS-containing medications in a similar manner. Patients

will be included in the analysis only once. As patients could conceivably qualify as new users more than once during the study period or be on more than one medication during the study period, the first prescription defining a patient as eligible for the study (either as new user of LABD or new user of ICS) during the study period only would be evaluated. As patients generally tend to fill multiple prescriptions for COPD in a year and add therapies rather than switch therapies in COPD, subsequent prescriptions would not be evaluated for new use moving forward to the end of available data, as this is expected to yield few patients. In the case of data anomalies where a patient is prescribed ICS/LABA fixed dose combination with either LABA or ICS monotherapy, the patient will be considered as having an ICS/LABA new user prescription.

The date when patients become new users of LABD or ICS-containing medications is considered the **Cohort Entry Date**.

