5.7.2. Patient Follow-up Time from Cohort Entry

Patients will be followed from the date of their first eligible prescription (New User entry date) until the earliest of the following:

- date of treatment end (up to 90-day gap allowed for each inhaler),
- date of study end point (first pneumonia event of interest)
- date of transfer to a new practice / practice stops participating or CPRD ends,
- date of ICS initiation (among LABD new users)
- death or
- HES data ends (last available HES data)

As part of the primary analysis, patients will be examined for their first pneumonia (severe CAP, HAP, or non-severe CAP). For example, a patient who has HAP and then

another year has a severe CAP would be considered only for his first event, the HAP. For the analysis of severe CAP, this same patient would be censored on the start date of their HAP episode.

Each patient will have a time and "censoring" variable, which is an indicator variable (yes/no) that indicates 1 if they have had the event of interest or 0 if they are censored. Time will be calculated as the date of the event or censoring minus the cohort entry date plus 1.

Incidence rates of the pneumonia outcomes will be calculated as the number of patients experiencing an event divided by the person-years at risk. Incidence rate ratios were calculated as the incidence rate in the ICS-containing group divided by the incidence rate in the LABD group. Precision of effect estimates will be evaluated from the width of the 95% CIs.

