Parameterization of the explanatory variables in the propensity score generation and subsequent modeling will be based on determining the most appropriate measure (e.g., number of moderate exacerbations may be collapsed into ordinal categories or yes/no if there are few patients with more than 1 in the Baseline Period.) Imputation, removal of outliers, and parameterization of variables for the model will be described in the analysis plan and determined prior to fitting final outcome models.

For the primary analyses (severe CAP and HAP combined), patients will be followed using a Cox proportional hazards model until they experience the first of the following events or censoring: (1) pneumonia event of interest (based on their first pneumonia episode following Cohort Entry), or censoring for (2) death (competing cause), (3) other pneumonia event of interest prior to severe event (competing cause), (4) cohort exit / transfer, practice stopped participating, or end of CPRD follow-up, (5) new user treatment ends, (6) LABD new user is prescribed an ICS, or (7) end of HES follow-up (). Each patient will have a time and "censoring" variable, which is an indicator variable (yes/no) that indicates 1 if they have had the event of interest or 0 if they are censored.

For the analysis of all pneumonia patients will be followed using a Cox proportional hazards model until they experience any pneumonia event (as their first pneumonia episode) or censoring.

To test proportionality of the hazard functions, model diagnostics will be evaluated by including time-dependent covariates in the Cox model. The primary outcomes will be severe pneumonia, (defined as severe CAP and HAP). As a secondary analysis, all pneumonia will be examined.

If one of the explanatory variables is not proportional, we will consider alternatives (time-dependent variable for the non-proportional predictors or stratification on the non-proportional predictors).

If the number of confounders requires reduction to be supported in the Cox model (based on feasibility), a variable selection strategy may be employed as described in the analysis plan.

Interactions between explanatory variables will be determined based on available theory and include ICS/LABD medication use by known risk factors for pneumonia (BMI, age, GOLD stage III/IV, MRC \geq 4, history of pneumonia, current smoking status, deprivation quintiles). Additional interactions may be evaluated with ICS and other patient characteristics.

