5.7.5. Additional Multivariable Analyses

All pneumonia events will be combined as a secondary pneumonia outcome. Multivariable modeling will be employed on this outcome (all pneumonia) in the same manner as applied to the primary severe pneumonia outcome.

To examine a potential dose-response relationship with ICS-containing medications, the strength of the prescribed ICS medication on the Cohort Entry Date will be categorized into equipotent doses of low, medium, and high-dose ICS based on classification according to Figure 3-1 presented in the Global Initiative for Asthma (GINA) guidelines [GINA, 2011]. The strength of the new user prescription would be entered into the Cox model primary outcome models as low, medium, and high relative to LABD (e.g. dummy variables). Cumulative dose may be considered.

To identify more persistent users, the primary endpoint (severe pneumonia) will be evaluated restricting to patients who are prescribed treatment for greater than 6 months (allowing for 90-day gaps between treatments). Each inhaler can last up to 90 days.

As there may be differential drop out over time, ICS-Containing vs. LABD new users who continue taking medications for at least 6 months may not be clinically similar. Therefore, additional confounders will be identified in the 6-mo period to account for any events that would affect censoring or outcomes (e.g., COPD exacerbations, emergency and non-emergency hospitalization, primary care visits). The PS will be regenerated among the more persistent group to include updated confounders measured in the 6-mo period of persistent use as the new analysis "start". Patients who have an unresolved episode of pneumonia after 6 months of persistent use would be excluded from the persistent analysis. Patients would be required to have at least 14 days between their last pneumonia episode and the persistent analysis "start" date.

All analyses will be performed using SAS [Cary, NC].

If there is sufficient sample size, MRC dyspnea score will be included as a confounder in the primary model (collected 2009 onwards) as part of secondary analyses. Otherwise, it will not be included.

To examine potential differences in patient groups, demographic characteristics of patients with HES linkage vs. those without HES linkage will be compared. It is not expected that there will be clinically significant differences between these groups.

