As a result of the subsequent feasibility prior to the conduct of the study, this protocol was amended to improve precision. The study period was expanded to include more patients and pneumonia events. In addition, the pneumonia endpoints were grouped as severe events (1 HAP and all severe CAP combined). In addition, an overall pneumonia outcome was included rather than severe CAP and non-severe CAP in order to improve on precision and to inform on pneumonia overall. There are also known limitations of database analyses, including the potential for confounding by severity. ICS-containing medications may be dispensed to patients who have more severe COPD or those at higher risk for exacerbation than patients who are receiving long-acting bronchodilators alone. In this study, we will adjust for disease severity in the year prior to initiation using propensity scores, including lung function, exacerbation history, pneumonia history, smoking status, and treatment. Only diagnosed diseases are recorded in CPRD-GOLD. Medication use in CPRD-GOLD is based on prescribed medications recorded by the GP. which might not have been dispensed at the pharmacy or ultimately utilized by the patient. Diagnostic practices for pneumonia may be different in the UK compared with other countries limiting the generalizability. A final disadvantage is that this study does not include the investigational combination inhaled medication FF/VI, but rather can only examine approved ICS-containing medications in this retrospective cohort design.

When identifying pneumonia in databases, definitions are based upon existing information collected in routine healthcare which may not include all details measured in clinical trials. In addition, there is lack of agreement between pneumonia classification in the absence of chest x-rays, sputum, etc. Our definitions were based on using HES for hospitalization and built upon prior work (including validation of severe CAP). There may be some confusion between diagnoses of pneumonia versus influenza-related morbidity.

Despite the limitations, this study will provide insights into risk factors for all pneumonias and severe pneumonia, including whether ICS modify the effect of risk factors for severe pneumonia. The results may identify more specific patient groups that are at greatest risk of severe pneumonia and may identify where risk minimization and/or medical recommendations may be appropriate.

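### Censoring LABD users at ICS start, with no counterpart for ICS users who escalate, is potentially informative and probably inflates the primary hazard ratio by an unknown amount

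*Protocol*

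**What the plan says.** Section 5.7.2 lists what ends follow-up. One reason applies to the LABD arm alone: "date of ICS initiation (among LABD new users"). Section 5.7.4 carries it into the primary model as censoring reason "6) LABD new user is prescribed an ICS". The only treatment-related reason common to both arms is the "date of treatment end (up to 90-day gap allowed for each inhaler"). Neither list mentions an ICS user who adds a LABA or LAMA or moves to a higher dose.

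Three other statements bear on what this rule does:

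- Section 5.2.1, on why treatment is stepped up: "If the disease severity warrants, adding additional therapy (a second bronchodilator or ICS) is recommended".
- Section 5.2.1, on how: patients tend to "add therapies rather than switch therapies in COPD". Each patient also enters the analysis only once.
- Section 1, on risk factors for pneumonia, which include "higher levels of dyspnoea, and markers of COPD disease severity".

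On adjustment, Section 6 says "we will adjust for disease severity in the year prior to initiation using propensity scores", and Section 5.7.4 builds the inverse-probability-of-treatment weights from baseline covariates. Post-baseline information appears only in the persistent-user analysis of Section 5.7.5, where "additional confounders will be identified in the 6-mo period to account for any events that would affect censoring or outcomes".

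**The concern.** A Cox model treats censored patients as if, given the covariates used, they had the same future risk as those who remain. By the protocol's own account, an LABD user who is given an ICS has often worsened, and worse disease carries more pneumonia. Such a patient leaves the LABD risk set, and because nobody enters twice, a later pneumonia counts in neither arm. An ICS user who worsens to the same degree and adds a bronchodilator normally keeps the ICS, stays on treatment and stays at risk.

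The treatment weights balance the arms at entry only. As follow-up proceeds, the LABD risk set can lose its higher-risk members while the ICS risk set keeps them. Part of any excess hazard would then come from the censoring rule and not from ICS. The result goes to regulators (Section 3) and will be read against the margin of 2.0 for severe pneumonia in Section 5.7.8, so a modest inflation can matter.

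**Working it through.** **1. The plan's own figures.** The protocol gives no figure for this bias, so there is none to reproduce. Its precision figures do reproduce. For severe pneumonia, 6,600 × 4/1000 + 12,000 × 7.4/1000 = 26.4 + 88.8 = 115.2 events (stated 115), and a two-proportion calculation gives 82.8% power (stated 82%). For all pneumonia the results are 269.4 events (stated 270) and 85.3% power (stated 85%). None of these depends on the censoring rule.

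**2. Follow-up time.** Pooled rates and event counts imply 106/5.3 × 1000 = 20,000 person-years and 283/15.8 × 1000 ≈ 17,911. Over 18,742 patients that is 1.07 and 0.96 years each. A treatment-end rate of μ = 0.9 per year gives a mean of about 1.0 to 1.1 years.

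**3. Assumptions (not in the documents).** Patients deteriorate at rate δ per year (0.1 to 0.4). Afterwards the pneumonia hazard is R times higher (1.5 to 3). A share q of deteriorating LABD users starts an ICS at once and is censored (0.5 or 0.8). Deteriorating ICS users stay in. The true hazard ratio is 1.0.

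**4. Model.** Let s = exp(−δt). With ICS share 0.645 (12,000 of 18,600), the numbers at risk are proportional to:

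- ICS: Y1 = 0.645·exp(−μt)
- LABD: Y0 = 0.355·exp(−μt)·[s + (1−q)(1−s)]

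The event intensities are proportional to:

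- ICS: e1 = 0.645·exp(−μt)·[s + R(1−s)]
- LABD: e0 = 0.355·exp(−μt)·[s + R(1−q)(1−s)]

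The apparent log hazard ratio β solves ∫ {e1 − (e0 + e1)·Y1·exp(β)/[Y0 + Y1·exp(β)]} dt = 0.

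**5. One time point as illustration.** Take δ = 0.2, q = 0.8, R = 2 at one year, so s = 0.819. In the ICS arm 18.1% of those at risk have deteriorated, and the mean relative hazard is 1.181. In the LABD arm the share is 0.036/(0.819 + 0.036) = 4.2%, and the mean is 1.042. The ratio is 1.181/1.042 = 1.13 with no drug effect.

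**6. Apparent Cox hazard ratio, true value 1.0.**

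| δ per year | q | R = 1.5 | R = 2 | R = 3 |
|---|---|---|---|---|
| 0.1 | 0.5 | 1.02 | 1.04 | 1.08 |
| 0.1 | 0.8 | 1.04 | 1.07 | 1.14 |
| 0.2 | 0.5 | 1.03 | 1.06 | 1.12 |
| 0.2 | 0.8 | 1.06 | 1.12 | 1.22 |
| 0.4 | 0.5 | 1.05 | 1.08 | 1.14 |
| 0.4 | 0.8 | 1.09 | 1.16 | 1.30 |

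In the central case (0.2, 0.8, 2), a true 1.50 appears as 1.67 and a true 1.85 as 2.06.

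**7. What removes or shrinks it (central case).**

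- Same censoring at deterioration in both arms: 1.00.
- No change in hazard after deterioration (R = 1): 1.00.
- Hazard falls afterwards (R = 0.8): 0.98.
- Half as many ICS escalators also censored: 1.06.
- Deteriorated patients in both arms leave treatment at 2 per year: 1.07.

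**8. Scale.** With 106 events, the 95% interval multiplies and divides the hazard ratio by exp(1.96/√(106 × 0.645 × 0.355)) = 1.49. A true 1.25 has an upper limit of 1.25 × 1.49 = 1.86, below 2.0. Inflated by 12% to 1.40, the upper limit is 1.40 × 1.49 = 2.09, above it.

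**The case against.** The rule follows from the exposure contrast. An ICS user who adds a bronchodilator is still exposed to ICS; an LABD user who starts an ICS is no longer unexposed, and keeping that time would misclassify it. This stands: a reader might infer that the rule should be dropped, but dropping it would pull the estimate toward 1.

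A reader might also infer that the hazard ratio is shown to be biased upward, or that time after deterioration counts mainly in the ICS arm. The documents support neither.

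- They give no step-up rate in either arm and no pneumonia risk after step-up. The direction is an expectation that rests on a higher hazard after step-up.
- The step-up described in Section 5.2.1 may be a second bronchodilator. LABD users who take that route stay in follow-up, as does any time between worsening and ICS start.
- The protocol does not say whether a move from ICS monotherapy to ICS/LABA ends new-user treatment. If it does, some ICS escalators are censored too.

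The model is also harsh, since it censors at the moment of worsening and makes the raised hazard permanent. In a crude rate-ratio version with one year of mean follow-up, the central case is 1.12. It falls to about 1.03 if the raised hazard lasts three months on average, and to about 1.09 if the ICS starts three months after worsening. That version reaches 1.37 only with every input at its extreme (δ = 0.4, q = 0.8, R = 3), and it is a rate ratio, not the Cox estimate.

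Finally, the protocol is not blind to the issue. Section 5.7.5 recognises differential drop-out, the Table 10 shell counts LABD users censored at ICS start, and modelling detail is left to the analysis plan. But the Section 5.7.5 remedy covers persistent users only. Table 10 is not split by arm and has no row for ICS escalation. The first-year comparison that ignores censoring (Section 5.7.6) leaves treatment out. The one-sided rule is fixed in the protocol text, so it is not merely detail still to come.

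**Conclusion.** The point holds as potentially informative, one-sided censoring that the stated baseline weighting cannot correct. Under the protocol's own premises, the ICS versus LABD hazard ratio for severe pneumonia is expected to be biased upward. The amount is unknown: about 1.02 to 1.30 at a true 1.0 over the assumed range, about 1.12 in the central case, and nil if the hazard does not rise after step-up. LABD users who add a second bronchodilator, and any ICS escalators treated as ending treatment, reduce the size. On the log scale the central bias is ln 1.12/ln 1.49 = 0.28, a little over a quarter of the half-width of the confidence interval. That is not dominant, but it is enough to change whether a margin of 2.0 is excluded. Severity: should fix before analysis, with moderate confidence.

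**What to change.** 1. Keep censoring at ICS start. In the primary Cox model, multiply the treatment weights by inverse-probability-of-censoring weights for treatment-related censoring. Base them on time-updated exacerbations, oral steroid and antibiotic prescriptions, GP visits and admissions, all available in CPRD-GOLD and HES.
2. Name two sensitivity analyses: as-initiated over the first 12 months, with no censoring at step-up or treatment end in either arm; and the same censoring at escalation in both arms, with escalation defined beforehand.
3. State whether moving from ICS monotherapy to ICS/LABA counts as treatment end.
4. Split Table 10 by arm and add a row for escalation in the ICS arm.
5. Do not make agreement between the analyses a condition for believing an ICS effect. Crossover dilutes the as-initiated estimate, so the two should differ if ICS harm is real. Interpret differences in that light.

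The cost is protocol and analysis-plan wording plus programming on data in hand. The censoring weights will widen the interval slightly.
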